5.7 Bias in data collection, measurement and analysis

There is potential for bias in data collection, measurement and analysis in this study, which we will make every effort to curtail. Bias in *data collection* is the most likely to be a problem in our study. Selection bias in terms of our initial qualitative interviews (Phase I) and RCT participants could occur, as those YBMSM more interested in our project may already be likely to have higher levels of social capital and be more engaged in care. Given this concern, we propose to expand beyond recruiting at CBOs and in the clinic, and also recruit in more general community settings and online. In terms of *measurement*, our primary outcome will be measured using the MSCS, which has only had limited use in the YBMSM population. Although our preliminary analyses have shown good reliability in other YBMSM samples, it will be important to continue to examine the performance of this measure in this population. Finally, in terms of *analysis*, the qualitative analysis is prone to bias given the inherent subjectivity in qualitative research. In order to counteract this, we will utilize a team approach to qualitative coding and interpretation, and we will

undertake member checking with our YCAB to ensure that our interpretation of our qualitative data is consistent with their general experiences.

5.8 Intermediate reviews and analyses

As this is not a clinical trial with potential for physical harm, it is unlikely that any interim analyses of efficacy (significant differences in social capital improvement between the two arms) would cause us to halt the trial prematurely (either for no benefit or significant benefit from the social capital intervention). However, there are other reasons to conduct interim reviews and analyses as the trial progresses; namely: to review comparability of the intervention and control arms, to review retention and participant accrual rates, and to review quality of the data. We will plan to review our enrollment data on a weekly basis; our project coordinator will generate reports of numbers enrolled and rate of completing follow-up visits and present them at our weekly team meeting. Our biostatistician will also generate summaries of our enrollment, retention, and baseline survey responses every 3 months. Additional analyses may be undertaken for the purpose of presentation in national and international scientific meetings.

5.9 Limitations of study:

There are several limitations to this study. Recruitment and retention have the potential to be challenging among YBMSM living with HIV. In terms of initial recruitment, subjects who are newly diagnosed or re-engaging in care may decline participation due to challenges coping with new information, denial and/or grief in response to their new diagnosis. Experienced personnel and dedicated coordinators will be used to maximize recruitment. We are also planning to recruit from a wide range of venues including the Grady IDP clinic and our partnering community-based organizations. If enrollment is still inadequate, which is unlikely, we also have relationships with other clinical sites in Atlanta that care for HIV-positive YBMSM aged 18-29 (the Emory Midtown Hospital HIV clinic, Atlanta Veterans Administration Hospital, Fulton County Health Department) and could look into expanding recruitment to those sites.

5.10 Identifying, managing, and reporting adverse events:

Study staff will be instructed to notify the PI immediately via phone or pager if there is any adverse event, whether or not they perceive it to be related to study participation. The project coordinator will then take the responsibility of reporting to the Emory IRB within 24-48 hours. Additionally, the project staff member who witnessed the event will complete an Adverse and Negative Events Form (Appendix H) that includes the date, a description of the event, duration, severity, actions taken to remedy the negative event (including professional referrals). Adverse events will also be reported to the CDC.

5.10.1 Specific procedures for handling reports of psychological distress:

There is a risk of uncovering information about psychological distress during the qualitative interviews, as questions about social support networks (or lack thereof) and coping with HIV can be sensitive topics for some. Prior to beginning the study, research staff will receive sensitivity training from mental health providers at the IDP clinic, in order to be knowledgeable of psychological occurrences that require

intervention by a mental health professional. Any assessment of a potential psychological emergency during the course of the trial will result in the patient being transported to the Crisis Intervention Service unit at Grady Hospital, a 24-hour psychiatric emergency service with the ability to evaluate and stabilize patients. If less emergent emotional distress is noted, staff will be equipped with pamphlets listing mental health resources in the community and will assist with referrals as needed.

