2.5 Description of risks (physical, social, psychological, economic, other) to individual or group: Risks to participants from a physical standpoint are minimal, as there are no medical procedures being conducted in this study. There are risks from a social and/or psychological standpoint, primarily related to the potential for a breach of privacy which could lead to inadvertent disclosure of HIV status or sexuality. One source of such a breach could be study records; we will take the necessary precautions to prevent this including password protection of all participant records and de-identification of datasets before analysis. A second source of such a breach is other participants, as the activities include involvement in a group project with other HIV-positive individuals. We will make sure to explicitly discuss privacy concerns and instruct participants not to disclose others' participation and/or HIV status; however this will be impossible for us to enforce. We will ensure that participants are aware of this potential risk in the informed consent process.

2.6 Description of anticipated benefits to the research participant: If our intervention is effective, it will provide direct benefits to the participants in terms of improved social support, social capital and HIV related outcomes. Those in the control arm should also receive the benefits of a health education intervention that will improve their knowledge about HIV and other health issues.

2.7 Emergency care: Given the non-invasive nature of this study, it is not expected that involvement in either the control or treatment arm would lead to any physical or psychiatric emergencies. However, were an emergency to occur during the course of involvement, study staff would be instructed to contact the PI immediately via cell phone or pager. [name] would then direct the participant to either the ER (including Grady Psychiatric Emergency Services if applicable) or their primary medical provider, and she would also record the adverse event for immediate reporting to the Emory IRB (Adverse Event form in Appendix H).

2.8 Study time line:

Activity	Pre-Award	Year 1	Year 2	Year 3	Year 4
Research Activities					
Team consolidation, hiring new staff, planning					
Development of project guidelines/SOPs					
IRB review: Emory, Grady					
IRB review/project determination review: CDC					
Qualitative interview guide development					

Aim 1: IDIs with YBMSM												
Aim 1: IDIs with CBOs, providers												

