maximize retention will also include maintaining a database of participants' phone numbers and email addresses. In order to minimize the risk of a privacy breach with any of these files, participants will be assigned a subject ID number which will be used to identify them in the database. Only one file will link the subject ID number to the participants' medical record number, and all files will be password protected, kept on a secure server, and only accessible to the study team. Study files will be kept in password protected files within HIPAA compliant shared drive folders only (e.g. Emory Box). Any paper documents (such as signed informed consent forms) will be kept within a locked file cabinet in the PI's locked office accessible only to key research staff.

5.5. Information management and analysis software:

Data will be collected and stored electronically using the RedCap (Research Electronic Data Capture) program. RedCap is a secure web application for building and managing online surveys and databases. It is compliant with the requirements of HIPAA and therefore ideal for the collection and storage of personal health information such as that which we will be collecting here.

Software for data analysis will include statistical software (SAS, SPSS) as well as qualitative data management software (MaxQDa). We will de-identify all qualitative and quantitative datasets before beginning analyses and will only maintain the de-identified datasets once data collection is completed.

5.6 Quality control/assurance:

All data will be collected by trained staff members. [name] will assume primary responsibility for training and supervision of research staff administering the recruitment, informed consents, and Redcap online questionnaires. Staff will meet for weekly supervision with [name] and her mentors to discuss research protocol and logistical issues, as a way to allow for discussions of adverse events and promote maintenance of study integrity. Data will also be checked periodically for consistency and quality, as described in the *Data entry, editing and management* section above.

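### Disclosure of HIV status or sexuality is the primary non-physical risk the protocol names, but no described visit or measure asks about it, so such events are likely to be under-recorded, possibly unequally by arm

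*Combined protocol and SAP*

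**What the plan says.** Section 2.5 treats physical risk as minimal and describes the social and psychological risks as "primarily related to the potential for a breach of privacy which could lead to inadvertent disclosure of HIV status or sexuality". It names two sources. The first is study records, which are to be protected by passwords and de-identification. The other is the group itself: "A second source of such a breach is other participants, as the activities include involvement in a group project with other HIV-positive individuals". Participants will be told not to disclose one another's participation or status, with the admission that "however this will be impossible for us to enforce".

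Section 5.10 requires staff to "notify the PI immediately via phone or pager if there is any adverse event, whether or not they perceive it to be related" to participation. A report to the IRB follows within 24-48 hours, and events also go to the CDC. In addition, "the project staff member who witnessed the event will complete an Adverse and Negative Events Form", which records the description, duration, severity and action taken. Section 5.10.1 deals with distress uncovered during the qualitative interviews.

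Section 5.8 gives the reasons for interim review: "to review comparability of the intervention and control arms, to review retention and participant accrual rates, and to review quality of the data". The biostatistician will produce "summaries of our enrollment, retention, and baseline survey responses every 3 months". Section 5.6 provides weekly staff supervision, "as a way to allow for discussions of adverse events and promote maintenance of study integrity".

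**The concern.** Where a protocol admits that it cannot enforce prevention of its primary non-physical risk, it depends on detection. Staff are with participants for a one- or two-day meeting and then at survey visits up to 10 months. A disclosure by a fellow group member would most plausibly happen elsewhere. That is an inference, since the documents do not say where breaches occur. Such an event enters the record only if the participant volunteers it.

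Two things are at stake. First, section 1.4 intends the intervention for use in other settings, and a low count from passive reporting would tell later users little about this risk. Second, the arms may not be recorded alike. Both meet in groups, but only the intervention arm has the 30-day challenge, and the B6 Addendum says its activities are meant to create new connections within groups. The Year 4 interviews (n=30) are also confined to interested intervention participants. Exposure and the opportunity to report could therefore both differ by arm.

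**Working it through.** The documents give no disclosure rate, adverse event rate or safety threshold, so there is no figure to reproduce. The check is mainly a comparison of text.

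**Routes by which a disclosure could be recorded**

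| Route | Section | Asks about disclosure? | Both arms? |
|---|---|---|---|
| Staff notify the PI of any event | 5.10 | No; staff must see it or be told | Yes |
| Event form | 5.10 | No; assigned to a staff witness | Yes |
| Survey visits | 2.3, 5.2 | None described; surveys and record releases | Yes |
| Table 2 measures | 4.2 | None listed; stigma, depression and distress are scales, not event records | Yes |
| Retention contacts | 2.3 | No; issues with trial procedures | Yes |
| Weekly supervision | 5.6 | No; discusses events already known | Yes |
| Year 4 interviews | 2.3 | Open-ended, on experience of the program | Intervention only |
| Three-monthly summaries | 5.8 | No adverse event item | n/a |
| Quantitative analysis | 5.2.1 | No adverse event summary by arm | n/a |

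Every route open to both arms depends on a staff member seeing the event or a participant volunteering it. If no staff member saw the event, 5.10 assigns the form to nobody.

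**Illustration of what a count of zero could show**

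Inputs: 60 per arm and 120 in total (section 2.3). The capture share c, the proportion of true events that get recorded, is an assumption; the documents give none.

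With zero events among n participants, full capture and independent events, the one-sided 95% upper bound u solves (1 − u)^n = 0.05, so u = 1 − 0.05^(1/n).

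- n = 60: 1 − 0.05^(1/60) = 4.9%.
- n = 52, applying the 87% retention quoted in section 2.3 from another trial (0.87 × 60 = 52.2): 1 − 0.05^(1/52) = 5.6%.

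If only a share c is recorded, the bound on the true rate is roughly u/c. The last column gives the chance that nothing is recorded among all 120 if the true rate were 5% (an assumed 6 events), which is (1 − 0.05c)^120.

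| Assumed c | Upper bound, 0 of 60 recorded | Chance of no record, 120 at 5% |
|---|---|---|
| 1 | 4.9% | 0.2% |
| 0.5 | 9.7% | 4.8% |
| 0.25 | 19.5% | 22% |
| 0.1 | 48.7% | 55% |

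Independence is doubtful, because one member of a group of about 10 could expose several others. The bounds would then be wider.

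**The case against.** The strongest reply is that 5.10 is broader than its form. The duty to notify covers any adverse event, related or not, and is not limited to witnessed events. A breach that a participant reports already goes to the PI, the IRB and the CDC, faster than any three-monthly table. This stands. A reader might infer from the witness wording that only witnessed events count; the documents do not support that. The wording leaves a gap in who completes the form, not in who must be notified. Nor can one say that later groups would run in ignorance of earlier breaches, since any breach reported to staff would be known.

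Other parts of the reply also stand:

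- Other participants are one of two named sources of the risk, not singled out as the main harm.
- Weekly supervision and retention contacts exist, and stigma, depression and distress are measured repeatedly.
- Section 5.8 is mainly about operational review, with harm handled in 5.10.
- No aim or analysis makes a safety claim, so it cannot be said that the trial would declare the intervention safe on this point.
- The survey (Appendix F) and event form (Appendix H) are not in the text, so an existing disclosure item cannot be ruled out.

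None of this supplies a question put to participants in both arms. Supervision and notification act on what is already known, and the scales do not record whether a disclosure happened or why. If Appendix F has such an item, 5.10 need only cite it, but the form assignment and the missing counts by arm would remain.

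**Conclusion.** The point holds in a limited form. Recording of the primary non-physical risk relies on chance observation or volunteered reports, the form has no owner when staff did not see the event, and no summary by arm is planned. Under-recording is likely and could be unequal between arms. It is tempting to go further and say that breaches will go largely unrecorded, or that a count of zero would exclude nothing. The documents support neither: the capture share is unknown, and a zero count would be wholly uninformative only if capture were zero. The 4.9% and 5.6% bounds, and the wider ones under partial capture, are illustrative only.

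The conclusion assumes that Appendices F and H contain no disclosure question and that breaches by fellow participants mostly occur away from staff. It does not affect the primary analysis of social capital. The change is worth making because prevention is conceded to be unenforceable and the surveys are already scheduled.

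**What to change.** - Unless Appendix F already contains them, add two items to the 1-, 4- and 10-month surveys, worded identically in both arms: whether anyone learned of the participant's HIV status or sexuality through the study, and whether anything negative happened because of taking part. State that a yes is handled under 5.10.
- In 5.10, assign the form to the staff member who witnessed or was told of the event.
- Add adverse event counts by arm and delivery group to the three-monthly summary in 5.8 and to the final report.

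The cost is modest but not nil. The survey becomes slightly longer. Responses entered on a tablet must be checked promptly, because a yes starts immediate notice to the PI and the 24-48 hour IRB report. More events will go to the IRB and the CDC. Randomization, sample size and the primary outcome are unchanged.

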6.0 DISSEMINATION, NOTIFICATION AND REPORTING OF RESULTS

Dissemination of the results in the scientific and local community is a critically important part of this process. We plan a three pronged approach that includes: (1) Community meetings at the midway point and at the end of the project. At these meetings (which we also plan to stream as a webinar), we will invite community members to hear about the status of our project, to ask questions and to provide feedback on next steps. We will invite all of the key informants from Phase 1 to these meetings and enlist the help of the YCAB in advertising to the audience who would find it most relevant. (2) Scientific publications: We will publish interim and final results of each phase in peer-reviewed publications. Where possible, we will try to publish in open-access journals to facilitate dissemination to those outside of academic institutions. (3) Presentations at Scientific meetings: We will also present interim and final results at national and international meetings such as the American Public Health Association and International AIDS Society meetings.

Appendix A: B6 Addendum

A result of phase 1 was the development of Brothers Building Brothers By Breaking Barriers (B6), a two-day, 10-module group-level intervention. B6 does not focus exclusively on HIV, but rather takes a more holistic approach to supporting youth and developing resilience. The B6 intervention modules aim to develop resilience at the individual level (exploration of black gay identity, development of critical self-reflection and coping skills), social network level (exploring strategies for navigating family relationships) and community level (developing strategies for navigating clinical spaces and plans for community participation). Most intervention activities are interactive, in order to facilitate new social network connections (social capital) within intervention groups. In summary, our intensive CBPR approach resulted in a novel, culturally-specific intervention designed to enhance resilience by augmenting social capital among YB-GBMSM living with HIV.

Based on the aforementioned qualitative content analyses, a condensed list of key programmatic recommendations was created for incorporation into the intervention (Table 1). Participants had favorable reactions to the idea of a social capital-based resilience intervention for YB-GBMSM living with HIV. The most commonly cited recommendation was to ensure that the intervention addressed the holistic health and well-being of the participants, and did not focus too narrowly on HIV-specific content. Participants also gave feedback about the manner in which the intervention should be delivered, citing the importance of balancing entertainment with the educational objectives.

Table 1. Key Recommendations from Qualitative Interviews

Content

• Find a way to treat the whole person• Teach about finances, school, health, wellness• Empower participants with skills to get support they need• Raise awareness and pride about black gay culture and history• Address stigma, internalized homophobia• Find ways to create connectedness between YB-GBMSM• Refer participants to other resources as needed, particularly mental health
Approach

• Engage participants, make activities interactive and entertaining• Group discussions• Be nonjudgmental, sex positive, don't try to change people• Consider judicious use of social media• Meet participants where they are in terms of interest in HIV care engagement

Using a process informed by Intervention Mapping, which is a planning approach that combines theory and evidence as the foundation for taking an ecological approach to assessing and intervening in health problems and engendering community participation (Eldredge, L. K. B., Markham, C. M., Ruiter, R. A., Kok, G., & Parcel, G. S. (2016). Planning health promotion programs: an intervention mapping approach. John Wiley & Sons.), we combined the qualitative findings, theoretical constructs and YCAB input to develop an intervention outline focused on the following overarching goals: (1) exploration of one's self and identities; (2) building bonding capital; (3) building bridging capital; and (4) sustaining connections. We used an Intervention Mapping- informed process to align the theoretical constructs of social capital and the feedback from the qualitative findings with specific intervention components and activities. Table 2 displays the intervention content and the learning goals and objectives for each of the 10 modules of the intervention.

Table 2. Intervention Course Agenda

Day 1	
Session 1	Welcome to B6
Module 1: Set the Stage	Welcome/Introductions Brotherhood Agreement Brother Bingo
Module 2: Who's on your team?	Social Capital Presentation (together we have more) Bound By Barriers
Session 2	Building Myself
Module 3: Who am I?	Worth a Thousand Words On the Flip Side Affirmation Activity
Module 4: Communicating my Needs	Love Languages Assertive Communication (Passive/Aggressive)*
Module 5: Critical Reflection/Problem Solving	Critical Reflection: What? So What? Now What?* What would you do?
Session 3	Building Bridges
Module 6: Breaking Barriers: Relationships	Who you gonna Call? Acting Out B6 Trivia Review Closing

Day 2	
Session 3 Continued	Building Bridges
Module 7: Breaking Barriers: Professional Settings	Welcome Back! Work/School Life (Critical Reflection/Problem Solving) Rep Your Clinic
Session 4	Building Bonds

Module 8: Black Gay Community	What is Black Gay Community? Role Models/Heroes Jeopardy
Session 5	Staying Connected
Module 9: Connecting the Dots	Goal Setting * Using my Social Capital (Support Web) Building the Other Brother
Module 10: My Social Capital	30 Day Challenge So I know it's real Conclusion
